### **Informed consent procedure**

All participants must give informed consent, or assent if underage, prior to undertaking study procedures and these informed consents and assents must be obtained by clinical site staff using approved processes. Signed consent and assent forms will be maintained in a secure designated location at the site.

Participants will consent or assent for 3 years initially, equivalent to 4 Annual Screening and 4 Annual Sampling Visits (i.e. year 0, 1, 2 and 3). They may renew their informed consent or assent in the fourth year in order to continue participating in the study.

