## 6. Study Design

### 6.1 Overall Study Design

This is a Phase 0 observational study.

**Recruitment:** Participants will be recruited at multiple sites in the UK, Europe, North America, South America and Australasia from among participants in the Enroll-HD study who will have had an Enroll-HD study visit within three months prior to the Annual Screening Visit.

**Study Visits:** Participants will attend two annual study visits: an Annual **Screening Visit** followed by an Annual **Sampling Visit**. During the Annual **Screening Visit**, which may coincide with an Enroll-HD visit, medical history, clinical and phenotypic data (including a screening blood sample) will be obtained. These data will determine participant eligibility for participation in the study and will be used in the analysis of biomarker data. Participants meeting the eligibility requirements of the study and willing to continue in the study, will return for an Annual **Sampling Visit** within 30 days of the Annual Screening Visit. During that visit, biosamples will be collected following a fast of at least 6 hours, or overnight: blood will be obtained via venepuncture and CSF will be obtained via lumbar puncture. Participants will be contacted by telephone approximately 24-72 hours after the Annual Sampling Visit. Some participants may be invited to return for an **Optional Repeat Sampling Visit** 4-8 weeks following the **Annual Sampling Visit** during their first year of enrolment.

Participants will attend annual visits at regular intervals after the first Annual Screening Visit (i.e. at 1, 2, 3 years and so on)  $\pm$  2 months. Participants will be encouraged to complete all annual visits; however, they are under no obligation to take part and will be able to skip an annual visit without being discontinued from the study. Participants who do not come for an Annual Sampling Visit for three consecutive years will be discontinued from the study, but they may enroll again at a later date, if they so consent. Participants who have already completed HDClarity Sampling Visits under earlier versions of this protocol may also participate in the longitudinal study if they meet the eligibility criteria. Enroll-HD visits will provide the clinical data for this study.

**Biosample Preparation:** Samples will be processed and stored as described in Sections 10.1, 10.2 and 10.3 until ready for analysis.

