### **8.1 Description of Study Assessments**

The Annual Screening and Annual Sampling Visits should be no more than 30 days apart. The Annual Screening Visit may occur on the same day as an Enroll-HD visit. The Optional Repeat Sampling Visit will occur within 4-8 weeks of the Annual Sampling Visit during the first year of enrollment. Participants will be encouraged to complete all annual visits; however, they are under no obligation to take part and will be able to skip annual visits without being discontinued from the study for up to three years.

Information regarding occurrence of adverse events (AEs) and Serious Adverse Events (SAEs) will be captured each year in the period from the Annual Screening Visit until the follow-up phone call after the associated Annual Sampling Visit (or Optional Repeat Sampling visit, if applicable). Duration (start and stop dates and times), severity/grade, outcome, treatment and relation to study procedures will be recorded on the electronic case report form (eCRF).

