### **16.4 Informed Consent Procedure**

All participants must give informed consent prior to undertaking study procedures and these informed consents must be obtained by clinical site staff using approved processes according to all applicable laws and regulations on GCP. At a minimum, the consent process will involve:

1. Provision of written, ERB and/or IRB-approved information about the study to potential participants;
2. Potential participants permitted sufficient opportunity to read the information and consider the options without maximum but with a recommended minimum of 24 hours;
3. Potential participants permitted sufficient opportunity to ask questions and receive satisfactory answers from the site study team;
4. Potential participants' comprehension verified before signing a consent form; and
5. The voluntary signing of a consent form and countersigning by the study site personnel undertaking the consent process.

In the event that a site wishes to enroll participants with impaired capacity, specific ERB and/or IRB approval will be sought in advance before such participants are enrolled and a Legally Authorised Representative will sign on behalf of the participant.

In the case of underage participants, consent will be obtained from the parent or guardian, together with informed assent from the underage participant in compliance with local regulations and requirements.

Informed consent obtained at the beginning of the study will be valid for three years. The participants will be re-consented for the study after that every fourth year should they wish to continue participation. The participant is encouraged to provide a CSF sample every year but are at no obligation to do so. If a participant does not attend an Annual Screening and Sampling Visit for consecutive three years, they will be discontinued from the study. They can re-enroll in the study if they wish to do so.

Signed consent forms will be maintained in a secure designated location at the site.

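### Does a skipped Year-4 visit leave a participant enrolled with no rule on renewing consent?

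*Protocol*

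**What the plan says.** **Consent term.** Section 4.2.1 (Informed consent procedure) has participants "consent or assent for 3 years initially, equivalent to 4 Annual Screening and 4 Annual Sampling Visits (i.e. year 0, 1, 2 and 3" and adds: "They may renew their informed consent or assent in the fourth year in order to continue participating in the study". Section 16.4 agrees: "Informed consent obtained at the beginning of the study will be valid for three years", followed by "The participants will be re-consented for the study after that every fourth year should they wish to continue participation". Footnote 1 to the Schedule of Events sets the same four-year cycle. Sections 4.2.1 and 16.4 both require consent before any study procedure.

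**Skipping visits.** Section 6.1 says of participants that "they are under no obligation to take part and will be able to skip an annual visit without being discontinued from the study", and that "Participants who do not come for an Annual Sampling Visit for three consecutive years will be discontinued from the study". Section 8.1 says they "will be able to skip annual visits without being discontinued from the study for up to three years". Section 16.4 repeats the trigger: "If a participant does not attend an Annual Screening and Sampling Visit for consecutive three years, they will be discontinued from the study". None of these makes an exception for a year in which consent is due.

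**Visit instructions.** In the Schedule, signed consent is marked only at Year-0 Screening. The column for Years 1, 2 and 3 marks confirmation of continued consent, and Section 8.1.1 likewise asks for confirmation at every Screening Visit after the first.

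**The concern.** A participant who attends through Year 3 and skips Year 4 is past the consent term but, under the skip rule, still enrolled. Two readings then seem possible.

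- **Continuation.** The participant returns at Year 5 or 6, the visit follows the Years 1-3 column, continued consent is merely confirmed, and the next signature falls due at Year 8. Lumbar punctures in Years 5 to 7 would rest on a signature given for Years 0 to 3.
- **New enrollment.** Because Section 4.2.1 ties continuing to renewal in the fourth year, participation ended at Year 4 and the return starts again in the Year-0 column.

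If both readings were open, sites could differ on the validity of consent, on the age limit of 18 to 75 (judged when consent is given, in the cohorts that have it), on access to the Optional Repeat Sampling Visit, and on the period over which SAEs are documented.

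**Working it through.** **1. The stated equivalence.** Annual visits fall nominally at months 0, 12, 24 and 36. Four visits lie within 3 × 12 = 36 months, so three years and four visits agree at nominal dates. With the ±2-month window, Year-3 Screening can fall in months 34 to 38, and Sampling can run to about month 39. Section 4.2.1 counts the Year-3 visits as covered, so that small overrun is harmless.

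**2. Can the situation arise?** The Year-4 window is months 46 to 50, after the 36-month term. Take Year 0 as attended and Year 4 as skipped, and apply the rule of three consecutive misses to the 2³ = 8 patterns for Years 1 to 3:

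- Years 2 and 3 also missed: 2 patterns, discontinued at Year 4 or already at Year 3.
- All others: 8 − 2 = 6 patterns, still enrolled.

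Someone last sampled in Year 3 is discontinued only after also missing Years 5 and 6. The Year-6 window closes at month 72 + 2 = 74, or about 75 with the 30-day sampling allowance. Enrollment can thus outlast the consent term by 74 − 36 = 38 to 75 − 36 = 39 months.

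**3. How many attendance histories?** For Years 1 to 7, 81 patterns avoid three consecutive misses. Those attending Year 4 number 7 × 7 = 49 (seven allowed patterns on each side), so 81 − 49 = 32 miss it. This counts patterns, not people. The protocol gives no skip rate, so 32/81 is not a frequency.

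**4. Do the rules give opposite answers?**

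| Question | Rule | Answer |
|---|---|---|
| Is the participant discontinued? | 6.1, 8.1, 16.4 | Only after three consecutive missed years |
| May a procedure be done? | 4.2.1, 16.4 | Only with consent; the first consent lasts three years |
| What if the participant wishes to go on? | 16.4 | The participant is re-consented |

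The skip rule neither lengthens consent nor authorises a procedure. Someone who comes back at Year 5 wishes to continue, so Section 16.4 calls for re-consent. Nor does Section 4.2.1 state the new-enrollment reading: renewal there is something participants may do, and the section does not say that enrollment ends at Year 4 or that later renewal is barred.

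**5. Do the four consequences follow from the skip?**

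- *Consent:* the problem exists only on the continuation reading without a signature, which step 4 rules out.
- *Age:* a participant aged 72 to 75 at first consent is 76 to 79 at an on-time Year-4 re-consent. Whether the age test restarts is a question for regular attenders too.
- *Optional Repeat visit:* it is by invitation, for up to about 20% of participants. It would come into play only if the return were treated as re-enrollment, which no section says.
- *SAE period:* the collection periods in Sections 8.1, 14.2 and 14.2.1 differ from one another without any skipped visit.

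**The case for a change.** The strongest reply is that site staff work from Section 8.1.1 and the Schedule, not from the ethics sections. Read literally, those obtain consent at the first Screening Visit and only confirm it afterwards, and confirmation is not the written process listed in Section 16.4. Re-enrollment is described only after three missed years, so a Year-5 return has no explicit home. Open-ended participation with permitted skipping makes a missed Year 4 foreseeable.

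Part of this stands. No sentence says that a participant who missed Year 4 signs again at the next attended visit, and the enrollment status of that return is undecided.

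The literal reading of Section 8.1.1, however, proves too much. It would also remove re-consent for participants who attend Year 4 on time, against footnote 1 and Section 16.4. It has to be read with those two, and once it is, late returners are covered in the same way. The Schedule column is headed for Years 1, 2 and 3, and nothing assigns it to a return after a missed renewal.

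**Conclusion.** No change to the plan follows. This is an unwritten detail in how two rules meet, and a site would fill it sensibly: consent must precede procedures, the first consent lasts three years, and anyone wishing to continue is re-consented, so renewed consent comes before any later sampling. Whether that return is continuation or re-enrollment is an administrative decision for the sponsor.

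The situation can occur in 6 of the 8 patterns in step 2, but how often is unknown because no skip rate is given. No sample-size figure, bias, conclusion or demonstrated safety outcome turns on it. A clarifying sentence would do no harm if the consent text were being revised anyway.

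The conclusion assumes that the fourth year means the Year-4 visit, as the Year 0 to 3 equivalence and footnote 1 suggest, and that the consent form, which is not shown, follows the same cycle.

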## **16.5 Data Collection, Retention and Monitoring**

### **16.5.1 Data Entry/Electronic Data Capture System**

The data are entered electronically via secure internet-based technology. Access to the eCRFs is limited by password and can only be authorized by the Chief Investigator and issued by the study administrator. Each Site Principal Investigator in this study can only see data on participants from their own site. The data managers who are responsible for the data quality and integrity have access to all sites' data. Clinical research monitors, who are responsible for monitoring data for site that are assigned, can only review the data from those sites. They are responsible for study monitoring and ensuring compliance with the study protocol.

### **16.5.2 Data Quality Control and Reporting**

After data have been entered into the study database, a system of computerized data validation checks will be implemented and applied to the database on a regular basis. Query reports pertaining to data omissions and discrepancies will be forwarded to the Site Principal Investigator and Study Central Coordination for resolution. The study database will be updated in accordance with the resolved queries. All changes to the study database will be documented.

### **16.5.3 Archival of Data**

The database is safeguarded against unauthorized access by established security procedures; appropriate backup copies of the database and related software files will be maintained. Databases are backed up by the database administrator in conjunction with any updates or changes to the database.

UCL and each participating site recognise that there is an obligation to archive study-related documents at the end of the study (as such end is defined within this protocol).

The Chief Investigator will archive the study master file at UCL for at least 20 years and in line with all applicable legal and statutory requirements. The Site Principal Investigator at each participating site agrees to archive his/her respective site's study documents for the period of time specified in the site agreement and in line with all applicable legal and statutory requirements.

### **16.5.4 Investigator Site Files**

Each site will maintain an Investigator Site File (ISF) containing all applicable regulatory, ethical and GCP documentation relating to the conduct of the study at the site. It will be the responsibility of each site's Principal Investigator to maintain this ISF.

### **16.5.5 Source Documents**

The Site Principal Investigator should maintain source documents for each participant enrolled in the study. Source documents such as local laboratory ranges and reports, participant charts and doctors' notes will be kept as part of the participants' medical records. For participants who do not have a medical record per se, another method of documentation and record keeping will be employed, along with the obligation to retain source documents, such as laboratory reports, for the period of time specified in the site agreement. Participant files including medical records and signed participant informed consent forms must be available for review in the event the site is selected for monitoring, audits, or inspections.

### **16.5.6 Monitoring**

The Sponsor is responsible for ensuring the proper conduct of the study with regard to ethics, protocol adherence, site procedures, integrity of the data, and applicable laws and/or regulations. At regular intervals during the study and following completion of the study, the Sponsor's study monitors will contact the study site via visits to the site, telephone calls, and/or letters in order to review study progress, eCRF completion, and address any concerns or questions regarding the study conduct. During monitoring visits, the following aspects of study conduct will be carefully reviewed: informed consent of participants, participant recruitment, participant compliance with the study procedures, source data verification, use of concomitant therapy by participants, AE and SAE documentation and reporting, and quality of data. Records pertaining to these aspects are expected to be kept current.

The Site Principal Investigator must make study data accessible to the clinical monitor, to other authorized representatives of the Sponsor, and to regulatory inspectors.

### **16.5.7 Data transfer**

In the study, data will be collected from participants in accordance with the participant consent form, participant information sheet (as applicable) and of this protocol.

The data will be appropriately sent to the data repository held and managed by service providers engaged by CHDI for storage and data monitoring, and for the purposes of the EU General Data Protection Regulation (GDPR), both CHDI and UCL will act as joint data controllers of such data for the study. Both CHDI and UCL have an appointed Data Protection Officer to assist with their respective responsibilities and as part of their obligations under the GDPR, will provide participants with information about data protection and privacy and transfer of data outside of the EU. Participants who were consented into the study before GDPR was in force will be provided with a supplemental notice containing this information.

The service providers engaged by CHDI will process, store and dispose of all study data in accordance with all applicable legal and regulatory requirements, including, as applicable, the Data Protection Act 1998 and the General Data Protection Regulation and any amendments thereto. All paper and digital records not uploaded to the study data repository will be retained at individual study sites in locked and/or password-protected form under the control of the Site Principal Investigators.

## **16.6 Biological samples (handling, processing and storage)**

In the study, cerebrospinal fluid, plasma, serum and cells from CSF will be collected from participants in accordance with the participant consent form and participant information sheet (as applicable) and shall include all tissue samples or other biological materials and any derivatives, portions, progeny or improvements as well as all participant information and documentation supplied in relation to them. The biological samples will be appropriately sent to BioRep, [name] (or such other selected biorepository), for cataloguing and storage of the samples to be carried out in accordance with the protocol and the informed consents. BioRep (or such other selected biorepository) will process, store and dispose of all samples in accordance with all applicable legal and regulatory requirements, including, as applicable, the Human Tissue Act 2004 and any amendments thereto. Samples obtained from the incomplete penetrance HD cohort will be reserved for specific studies on incomplete penetrance alleles.

## **16.7 Amendments**

Any amendments to the protocol will be written and approved by the Chief Investigator and CHDI. All amendments must be submitted to the Sponsor and IRB/ERB for approval prior to implementing the changes. In some instances, an amendment may require changes to the informed consent form, which also must be approved by CHDI and submitted for IRB/ERB approval prior to administration to study participants.

## **16.8 Record Keeping**

### **16.8.1 Participant Health Information**

The Site Principal Investigator agrees to comply with all applicable laws and regulations relating to the privacy of participant health information, including, but not limited to, the Standards for Individually Identifiable Health Information, 45 CFR Parts 160 and 164 (the Health Insurance Portability Accountability Act of 1996 [HIPAA] Privacy Regulation) and the EU General Data Protection Regulation (GDPR). Where applicable, the Site Principal Investigator shall ensure that study participants authorize the use and disclosure of protected health information in accordance with HIPAA Privacy Regulation and in a form satisfactory to the Sponsor.

### **16.8.2 Retention of Study Documents**

Study-related records must be retained for the period of time specified in the site agreement. The Site Principal Investigator must not destroy any study-related records without receiving approval from the Chief Investigator and CHDI. The Site Principal Investigator must notify the Chief Investigator in the event of accidental loss or destruction of any study records. If the Site Principal Investigator leaves the institution where the study was conducted, the Chief Investigator must be contacted to arrange alternative record storage options.

### **16.9 Reporting**

After completion of the study, an abbreviated clinical study report will be prepared by the Chief Investigator.

## 17. Appendix A – Site Principal Investigator Obligations

The study protocol and the final version of the participant informed consent form will be approved by an IRB/ERB before enrollment of any participants. The opinion of the IRB/ERB will be dated and given in writing.

The Site Principal Investigator will ensure that the IRB/ERB will be promptly informed of all changes in the research activity and of all unanticipated problems including risk to participants. The Site Principal Investigator will not proceed with changes to the protocol until IRB/ERB approval has been obtained.

Written informed consent must be given freely and obtained from every participant prior to clinical study participation. The rights, safety, and well-being of the study participants are the most important considerations and should prevail over interests of science and society.

As described in GCP guidelines, site personnel involved in conducting this study will be qualified by education, training, and experience to perform their respective task(s). Site personnel will not include individuals who (a) are currently and have not ever been, debarred or convicted of a crime for which a person can be debarred or otherwise suspended or disqualified under any applicable laws, regulations or professional guidelines or (b) have ever been threatened to be debarred or indicted for a crime or otherwise engaged in any conduct or activity for which a person can be debarred or otherwise suspended or disqualified. Quality assurance systems and procedures will be implemented to assure the quality of every aspect of the study.

### IRB/ERB Review/Approval/Reports

The protocol and informed consent for this study, including advertisements used to recruit participants, must be reviewed and approved by an appropriate IRB/ERB prior to enrollment of participants in the study. It is the responsibility of the Site Principal Investigator to assure that all aspects of the ethical review are conducted in accordance with the current Declaration of Helsinki, ICH, GCP, and/or local laws, whichever provide the greatest level of protection. A letter documenting the IRB/ERB approval which specifically identifies the study/protocol and a list of the committee members must be received by the Chief Investigator and CHDI prior to initiation of the study. Amendments to the protocol and informed consents will be subject to the same requirements as the original protocol and informed consents.

A progress report with a request for re-evaluation and re-approval will be submitted by the Site Principal Investigator to the IRB/ERB at intervals required by the IRB/ERCB. A copy of the report will be sent to CHDI and the Sponsor as well as letters of re-evaluation and re-approval.

After completion or termination of the study, the Site Principal Investigator will submit a final report to the IRB/ERB and to CHDI, if required. This report should include: deviations from the protocol, the number and types of participants evaluated, and significant AEs, including deaths.

